| Objectives | 
Primary To measure mucociliary clearance (MCC) in subjects with primary ciliary dyskinesia (PCD) caused by mutations in genes associated with a milder clinical phenotype and subjects with PCD caused by mutations in genes associated with a more severe clinical phenotype. To compare the 2 groups with each other and with healthy individuals.
 
Secondary To measure the effect of a short acting beta adrenergic (SABA) on MCC in subjects with PCD caused by mutations in genes associated with a milder clinical phenotype and subjects with PCD caused by mutations in genes associated with a more severe clinical phenotype.
 
Tertiary/Exploratory To measure cough clearance in subjects with PCD caused by mutations in genes associated with a milder clinical phenotype and subjects with PCD caused by mutations in genes associated with a more severe clinical phenotype.
 |
| Target Population | 
The target population is patients with PCD having confirmed mutations in genes associated with a milder clinical phenotype and subjects with PCD caused by mutations in genes associated with a more severe clinical phenotype. Subjects for this study will be recruited based on genotype.
 
Key Inclusion Criteria
 
PCD Patients
 
1. PCD subjects with mutations in genes associated with a milder clinical phenotype. This includes subjects with 2 confirmed mutations in RSPH1, RSPH9, RSPH4a, and DNAH11. This group may also include subjects with mutations in newly identified genes that are associated with a milder clinical phenotype. OR PCD subjects with mutations associated with a more severe clinical phenotype. This includes subjects with 2 confirmed mutations in DNAH5, DNAI1, CCDC39, and CCDC40. This group may also include subjects with mutations in newly identified genes that are associated with a more severe clinical phenotype.2. Age 12 - 90 years old3. Subjects of childbearing potential must be non-pregnant and non-lactating. 
Healthy Controls
 
1. ≥ 18 years old2. No pre-existing lung disease (asthma, cystic fibrosis, etc.)4. Subjects of childbearing potential must be non-pregnant and non-lactating. |

| | |
|--|--|

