9.1. Strategies that Apply to all the Specific Aims

To describe each measure of MCC by retention vs. time data set, the average % clearance (or 100* (1-Retention)) over the 0-60 and 60-120 min period of observation are computed (i.e. average of the 10 minute clearance values from 0 to 60 and 60-120 minutes). These computed values are signified as Ave60Clr and Ave120Clr respectively. Each calculated AveClr value utilizes all 10-minute data points, rather than simply reporting a clearance value at a single time, and represents the average clearance at the midpoint of each period of retention vs. time observation. 6 hour clearance is determined by (100* (1- 6 hour retention)) and provides an index of initial airway (6hr Clr) vs. alveolar (6hr retention) deposition that along with the central/peripheral (C/P) ratio provides regional deposition data that can be included as covariates in analysis of MCC comparisons between groups and within individuals.

Distributions of the outcomes is expected to be normal. We will plot the data in histograms and qqplot to evaluate any extreme datapoints or outliers. Their impact if any will be analyzed by performing the analysis with and without these datapoints.

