9.2. Description of the Study Cohort

The study cohort will consist of 12 PCD subjects with mutations in genes associated with a mild pulmonary phenotype (RSPH1, RSPH9, RSPH4a, or DNAH11) and 12 PCD subjects with mutations in genes associated with a more severe pulmonary phenotype (DNAH5, DNAI1, CCDC39, or CCDC40). A subject with mild pulmonary phenotype will typically have later onset of respiratory symptoms, better lung function, and milder bronchiectasis [4]. The age of patients will range between 12-90 years old. Eight healthy patients will be enrolled and undergo the same MCC protocol to obtain data for comparison. All subjects following the protocol will be included in the database. Subjects not

completing the protocol will be replaced. Baseline measurements of population (age, gender, race, FEV1) will be tabulated, for the whole population and per group (mild genotype, severe genotype, healthy) using mean and standard deviation and frequencies with percentages as appropriate. Data will be plotted in graphical figures including as histograms, bar plots, and scatter plots.

9.3.Aim-Specific Plans

Aim 1: To estimate how MCC measurements vary in PCD subjects with mutations in genes that are associated with mild or severe disease, relative to healthy subjects, and compare the 3 populations in term of Average Clearance.

Aim 1 is measuring MCC in PCD subjects having confirmed mutations in genes associated with a milder clinical phenotype and subjects with PCD caused by mutations in genes associated with a more severe clinical phenotype. These measurements will be reported as estimates of the means and standard deviations of Ave60Clr for each group, with associated confidence intervals. The baseline MCC in PCD subjects with “mild genotypes” and “severe genotypes” will be compared to healthy subjects. Our expected result is that subjects with mutations in genes associated with mild disease will display lower MCC rates than healthy subjects, and subjects with mutations in genes associated with severe disease will be even lower. For this comparison, we will use an ANOVA followed by multiple comparisons, using the Tukey Kramer correction. Then, to control for other possible sources of variations, age, gender and the initial deposition C/P will be added as covariates to PCD groups in a linear regression model on MCC.

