Aim 2: To characterize the effect of a short acting beta agonist (SABA) on MCC in PCD subjects with mutations in genes that are associated with mild or severe disease, and compare the 2 populations in terms of change in Average Clearance.

In aim 2, we will be measuring the effect of albuterol on MCC in PCD subjects. We will look at the change between Ave60Clear (before albuterol) and Ave120Clr (after albuterol) for each subject. Estimates of the means and standard deviations with associated confidence intervals will be reported for each group. Using paired t-tests, we will verify if the change is significantly different than 0. The difference between the 2 PCD groups will then be analyzed with an independent t-test. Age, gender and the initial deposition C/P will be added as covariates to PCD groups in a linear regression model on MCC.

As this is not a randomized crossover design nor a parallel-arm design, our proposed comparison pre- to post-albuterol is uncontrolled and cannot assess the efficacy of SABA. The goal of our study is to obtain first estimates of the immediate effect albuterol on MCC in a small, controlled population.

Aim 3: To characterize cough clearance in PCD subjects with mutations in genes that are associated with mild or severe disease, and compare the 2 populations in terms of change in Average Clearance.

We will compare cough clearance in PCD subjects with mutations associated with mild disease with PCD subjects with mutations in genes associated with more severe disease. Cough clearance will be measured as the change in retention between 120 and 150 min post deposition. This change between Ave120Clr and Ave150Clr will be tabulated for each PCD group in term of means and standard deviations with associated confidence intervals and compared to 0 using paired t-tests. The difference between the 2 PCD groups will then be analyzed with an independent t-test. Age, gender and the initial deposition C/P will be added as covariates to PCD groups in a linear regression model on MCC.

For all aims, all tests will be 2-sided, with $\alpha=0.05$. Tests with p values above 0.05 will be considered inconclusive.

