Expected results, potential problems, and alternatives. We expect to observe a significant rate of MCC (different from 0) in the group of PCD patients with mutations in genes associated with a milder phenotype. Based on previous studies of ciliary activity in PCD subjects with mutations associated with a more severe phenotype, we expect to see little or no MCC in this group of PCD patients. Further, we expect the rate of MCC to be significantly greater in subjects in the “mild genotype” group compared to the PCD patients in the “severe genotype” group. We expect that subjects with a mild genotype will respond to albuterol with an increase in MCC while the PCD patients with the severe genotype will not. We expect that subjects with mutations in genes associated with a mild phenotype will have better cough clearance compared to subjects with mutations in genes associated with a severe phenotype. As we have performed many similar studies in the past, including studies of MCC in PCD subjects, we anticipate no technical difficulties in carrying out these studies. If there is no difference detected between the groups of PCD patients, this would suggest that the less severe clinical phenotype observed in some patients is not due to the maintenance of a low level of MCC. Nevertheless, this would be an important experimental finding, as it would indicate that some other mechanism is responsible for the difference in phenotype.

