9.6. Sample Size Rationale

Sample size:

Based on the results of mucociliary transport (MCT) rates (healthy: 6.58 ± 1.39 , *Rspn1*^{-/-}: 1.63 ± 0.78 , other PCD: 0) in our mouse model [13], we expect subjects with a mild genotype to average 25% of the MCC of healthy subjects (healthy: Ave60Clr = $14.3 \pm 7.2\%$; mild expected: $3.6 \pm 2\%$), while subjects with a severe genotype will not show any MCC results, i.e. Ave60Clr not different from 0 (expected 0.5 ± 0.25). With $n=10$, we will be able to observe significant differences between all groups, with $\alpha=0.05$ and power=0.8.

Moreover, we expect the mild genotype group to react to albuterol treatment by doubling their Ave60 Clr, while the group with severe mutations will not. With 10 subjects, we will be able to find a significant response in the mild genotype group with expected Ave60Clr = $7.2 \pm 4\%$. Accounting for 20% possible dropout, we plan to enroll 12 subjects.

10. Safety Monitoring and Management

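### Aim 1 tests mild versus severe Ave60Clr in two ways without naming the deciding test, and at the plan's own values the two disagree in about 69% of trials

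*Combined protocol and SAP*

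**What the plan says.** The primary objective in the synopsis includes the contrast between the two PCD groups: "To compare the 2 groups with each other and with healthy individuals". Section 9.3 states the expectation directly: "we expect the rate of MCC to be significantly greater in subjects in the “mild genotype” group compared to the PCD patients".

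Section 9.3, Aim 1, gives that contrast two analyses. For the group comparison, "we will use an ANOVA followed by multiple comparisons, using the Tukey Kramer correction". Next, to control for other sources of variation, "age, gender and the initial deposition C/P will be added as covariates to PCD groups in a linear regression model on MCC". The synopsis repeats both steps.

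For every aim, "all tests will be 2-sided, with $\alpha=0.05$. Tests with p values above 0.05 will be considered inconclusive". Section 9.1 adds that extreme points will be looked for in plots, and "Their impact if any will be analyzed by performing the analysis with and without these datapoints".

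No section calls any of these analyses primary, supportive or sensitivity, or says what follows if they differ. The expected-results paragraph at the end of Section 9.3 does say how a null would be read. If no difference between the PCD groups is detected, this would suggest that preserved low-level MCC does not explain the milder phenotype, and the plan calls that an important finding.

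**The concern.** The genotype hypothesis rests on one contrast, and two tests of it stand side by side at the same threshold. They use very different error terms. Tukey-Kramer pools the variance of all three groups, including the highly variable healthy group. A regression confined to the PCD groups never sees that variance. If the two differ in power at the values the sponsor expects, one dataset will often give a significant regression and a non-significant Tukey comparison, and the report could rest on either. The plan's own reading of a null raises the stakes, because a non-significant Tukey result could be reported as evidence against the hypothesis while the regression supports it.

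**Working it through.** **Inputs.** Section 9.6 gives "healthy: Ave60Clr = $14.3 \pm 7.2\%$; mild expected: $3.6 \pm 2" and, for the severe group, 0.5 ± 0.25. I read the ± figures as SDs. Group sizes are 8 healthy, 12 mild and 12 severe (Section 9.2). Outcomes are taken as normal, as Section 9.1 expects. The covariates are an assumption: one binary and two continuous, unrelated to outcome and group.

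**The plan's own figure.** Section 9.6 claims power 0.8 for differences between all groups with n = 10, read as per group. Separate two-sided t-tests at n = 10 per group give about 0.98 to 1.00 for every pair, so 0.8 is met only as a floor. Under the planned Tukey-Kramer test at 10/10/10, simulated power is 0.99 for healthy versus mild, 1.00 for healthy versus severe, and 0.09 for mild versus severe. The claim fails for that last pair.

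**Tukey-Kramer at 8/12/12.**
- Pooled variance = (7 × 7.2² + 11 × 2² + 11 × 0.25²) / 29 = (362.88 + 44 + 0.69) / 29 = 14.05, so the pooled SD is 3.75. The healthy group supplies 362.88 of 407.57, or 89%.
- SE of mild minus severe = 3.75 × √(1/12 + 1/12) = 1.53.
- The Tukey critical value on the t scale (3 groups, 29 df) is 2.47, so the smallest significant gap is 2.47 × 1.53 = 3.78. The expected gap is 3.6 − 0.5 = 3.1.
- Power is 0.34 with the pooled SD held at 3.75, and 0.30 by simulation with it estimated.

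**PCD-only regression.**
- Pooled SD = √((2² + 0.25²) / 2) = 1.43.
- SE ≈ 1.43 × √(1/12 + 1/12) = 0.58, apart from a small loss to the covariates.
- Expected gap / SE = 3.1 / 0.58 ≈ 5.3.

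**Both tests on the same simulated data (20,000 trials per row).**

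| Setting | Tukey significant | Regression significant | Disagree |
|---|---|---|---|
| 8/12/12, regression in PCD only | 30% | 99% | 69% |
| 10/10/10, regression in PCD only | 9% | 98% | 88% |
| 8/12/12, regression in all three groups | 30% | 47% | 20% |

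In the PCD-only rows the disagreement is almost always a significant regression beside a non-significant Tukey result.

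**Sensitivity (values assumed).** Shifting one covariate by 1 SD between the PCD groups leaves disagreement at 67%. With a healthy SD of 4 it is 13%. With a common SD of 2 in all groups, Tukey is significant in 90%, the regression in 92%, and disagreement is 6%. Tukey power for mild versus severe is 0.69, 0.86 and 0.96 at healthy SDs of 5, 4 and 3.

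**False positives at 8/12/12.** With no true differences and equal variances, either test is significant for mild versus severe in about 5.3% of trials. The whole Aim 1 family rises from 5.1% with Tukey alone to 8.1% with the regression added. With healthy at 14.3 ± 7.2 and equal means in the two PCD groups, the either-test rate is 5.0% (both PCD SDs 2) to 6.1% (SDs 2 and 0.25).

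**One unequal-variance test of mild versus severe at 12/12.** Power is 0.998 by Welch and 0.99 by Games-Howell.

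**The case against.** The strongest reply is that the 69% is a power shortfall of the Tukey test, not a result of having two tests. That is right about the cause: remove the healthy group's excess variance and disagreement falls to 6%. It does not dispose of the point. Changing the pairwise method alone would leave two unranked tests, and ranking them with Tukey on top would leave the decisive test at about 30% power.

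A second reply is that the order of the text makes the ANOVA the main comparison and the regression a follow-up. The text gives an order and a purpose, but no status, and the 0.05 rule covers all tests.

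A third is that PCD-only is an interpretation. It is, although Aims 2 and 3 use the same phrase where only the PCD groups are analysed. Under the three-group reading the conflict shrinks to about 20% and does not vanish.

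A fourth is that this is a small first-estimate study whose compliance statement cites guidance against bright-line significance. Section 9.3 nevertheless sets a threshold and commits to a reading of a null.

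Three stronger readings are tempting, and the documents do not support them:
- A reader might infer that the plan delivers flatly opposite verdicts. By its own rule, p above 0.05 is inconclusive. The conflict becomes one of conclusions only through the expected-results paragraph.
- A reader might infer serious false-positive inflation. For mild versus severe it is negligible. The 8.1% needs healthy subjects to equal PCD subjects, which the plan does not expect.
- A reader might count the outlier reruns as further competing tests. Section 9.1 states no exclusion rule, so no error rate can be computed for them, and its wording already reads as a comparison of results with and without the points.

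**Conclusion.** The concern holds as an unranked pair of tests with very unequal power on the primary genotype contrast. At the plan's values and 8/12/12 they disagree in about 69% of trials under the PCD-only reading and about 20% under the three-group reading; at 10/10/10 with PCD-only it is about 88%. The harm is an unclear conclusion, and a stated Tukey test with about 30% power where Section 9.6 claims 0.8 for all groups. It is not excess false positives. The size rests on reading ± as SD, on normal outcomes, and above all on a healthy SD near 7.2; a smaller healthy SD shrinks it quickly.

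**What to change.** This part of the plan is wrong as written and should be corrected before the data are analysed. In Section 9.3, Aim 1, and in the synopsis:

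- Name mild minus severe Ave60Clr, in all evaluable subjects, as the decisive contrast.
- Test it with an unequal-variance method: Welch, or Games-Howell if all three pairs stay in one family. Power is about 0.99 at 8/12/12.
- Label the covariate regression, and in Section 9.1 the with and without outlier reruns, as sensitivity analyses reported as estimates with 95% CIs. State whether the regression covers PCD subjects only.

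A fixed-sequence order for the two healthy comparisons is optional. It is a trade-off, since Aim 1 is framed relative to healthy subjects.

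The cost is SAP wording, with no new subjects or data. The small downside is that a positive claim can no longer rest on the adjusted or outlier-excluded result alone.

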| 11.6. Safety Oversight | 32 |
| 11.7. Clinical Monitoring..... | 33 |
| 11.8. Quality Assurance and Quality Control | 33 |
| 11.9. Data Handling and Record Keeping..... | 33 |
| 11.9.1. Data Collection and Management Responsibilities | 33 |
| 11.9.2. Study Records Retention..... | 33 |
| 11.10. Protocol Deviations..... | 34 |
| 11.11. Publication and Data Sharing Policy | 34 |
| 11.12. Conflict of Interest Policy | 34 |
| 12. Additional Considerations..... | 34 |
| 13. References | 34 |
| 14. List of Appendices..... | 36 |

Statement of Compliance

This study will be conducted in accordance with the International Conference on Harmonisation guidelines for Good Clinical Practice (ICH E6) and the Code of Federal Regulations on the Protection of Human Subjects (45 CFR Part 46). The statistical analysis plans will be consistent with guidances such as the CONSORT Statement [1] or STROBE Statement [2], ICMJE recommendations [3], the 2016 and 2019 statements of the American Statistical Association [4,5], and recommendations in *Nature* [6,7].¹ All personnel involved in the conduct of this study have completed human subjects protection training.

¹ [1] www.consort-statement.org [2] www.strobe-statement.org [3] www.icmje.org [4] Wasserstein RL, et al. (2016), The ASA's Statement on p-Values, *The American Statistician*, 70:2, 129-133 [5] Wasserstein RL, et al. (2019), Moving to a World Beyond $p < 0.05$, *The American Statistician*, 73:sup1, 1-19 [6] Amrhein, et al. (2019) Scientists rise up against statistical significance, *Nature* 567, 305-307 [7] Editorial (2019) It's time to talk about ditching statistical significance: Looking beyond a much used and abused measure would make science harder, but better. *Nature* 567, 283-283.

Abbreviations and Definitions of Terms

| Abbreviation/Acronym | Definition |
|----------------------|---|
| AE | Adverse Event/Adverse Experience |
| AED | Automated External Defibrillator |
| ATS | American Thoracic Society |
| Ave60Clr | Average Clearance at 60 minutes |
| Ave120Clr | Average Clearance at 120 minutes |
| BP | Blood Pressure |
| CC | Cough Clearance |
| CEMALB | Center for Environmental Medicine, Asthma and Lung Biology |
| CF | Cystic Fibrosis |
| CI | Confidence Interval |
| CIOMS | Council for International Organizations of Medical Sciences |
| Co57 | Cobalt 57 |
| CONSORT | Consolidated Standards of Reporting Trials |
| C/P | Central/Peripheral |
| CRF | Case Report Form |

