| | Key Exclusion Criteria 
1. Clinically severe disease (requiring oxygen; FEV1<30%)2. Currently smoking or vaping3. Radiation exposure in the past year that would cause them to exceed federal radiation safety guidelines4. Free of sino-nasal pulmonary exacerbation for 4 weeks. |
| Numbers of Participants | Number to be recruited for screening : 40 Number of eligible participants enrolled: 32 |
| Clinical Phase | I |
| Intervention | Short acting beta agonist inhaler (albuterol by metered dose inhaler) |
| Study Description | Participants will inhale aerosolized radiolabeled sulfur colloid (Tc99m-SC) and will undergo gamma scintigraphy to measure mucociliary and cough clearance (MCC/CC) of the radiolabeled particles-from the airways. During the first hour of MCC imaging subjects will attempt to avoid coughing. Subjects will then inhale 4 puffs of albuterol (90 mcg/puff via metered dose inhaler (MDI) with spacer) to assess the effect of beta-adrenergic stimulation on MCC over the second hour of MCC imaging. After the two hours of MCC imaging. Subjects will perform spirometry and directed coughing over a 30-minute period during which CC will be measured, again by gamma scintigraphy. Subjects will then rest (approximately 3.5 hours) and be scanned for 15 minutes at 6 hour post initial MCC/deposition scan. |
| Outcome Measures | Baseline MCC: Ave60Clr Change in MCC following albuterol: Ave120Clr-Ave60Clr Change in MCC following cough clearance: Ave150Clr-Ave120Clr |
| Study Duration | The entire study is expected to last up to 4 years. |
| Subject Participation Duration | Each subject's participation will last 1 day. |
| Estimated Time to Complete Enrollment | 4 years |

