| Statistical Analysis Plans | Aim 1 will provide estimates of the mean and standard deviation of baseline MCC (Ave60Clr) for each group of PCD subjects. The 2 disease groups will be compared to data from healthy subjects using ANOVA followed by multiple comparisons, using the Tukey Kramer correction. Age, gender and the initial deposition C/P will be added as covariates to PCD groups in a linear regression model on MCC. In Aim 2, the change pre- to post-albuterol (Ave120Clr-Ave60Clr) will be calculated for each subject. Estimates of the mean and standard deviations will be reported for each group and compared with paired t-tests. The difference of change between the 2 groups will first be analyzed with an independent t-test. Age, gender and C/P will then be added as covariates in linear regression model. |

| | |
|--|--|
| | 
In Aim 3, the change pre- to post-cough clearance (Ave150Clr-Ave120Clr) will be calculated for each subject. Estimates of the mean and standard deviations will be reported for each group and compared with paired t-tests. The difference of change between the 2 groups will be analyzed with an independent t-test. Age, gender and C/P will then be added as covariates in linear regression model.
 
All tests will be 2-sided, with $\alpha=0.05$. Tests with p values above 0.05 will be considered inconclusive.
 |
|--|--|

2. Introduction: Background and Scientific Rationale

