4.1. Outcome Measures

Primary Outcome(s): Baseline MCC (Ave60Clr) in subjects with PCD caused by mutations associated with mild and severe clinical phenotypes.

Secondary Outcome(s): Change in MCC (Ave120Clr-Ave60Clr) after the administration of albuterol in subjects with PCD caused by mutations associated with mild and severe clinical phenotypes PCD patients with mild disease compared to PCD patients with more severe disease.

Tertiary/Exploratory Outcome(s): Change in cough clearance (Ave150Clr-Ave120Clr) in subjects with PCD caused by mutations associated with mild and severe clinical phenotypes PCD patients with mild disease compared to PCD patients with more severe disease.

5. Study Participants

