Prior to each MCC study, a transmission Co57 scan will be performed to define the lung boundaries, to assign regions of interest, and to normalize these regions for lung volume differences. A rectangular phantom containing the radioisotope Co57 (< 25 mCi) will be placed in front (5cm) of the subject sitting with his/her back to the gamma camera for 30 seconds. The transmission scan has been used by us (e.g., 05-2358, 08-0795, 06-1016, 13-1605, 15-938) and others to provide a delineation of lung boundaries for generating the central (C) and peripheral (P) regions of interest (ROIs) used to assess initial particle deposition (C/P ratio) and subsequent clearance of the inhaled radio-aerosol [15-16]. Prior to the transmission scan on each study day, we will place 2 spot markers of Americium241 (0.9 microcurie (uCi) each, gamma 66 KeV) on the upper and lower back of each subject during scanning (both Tc99m-SC deposition/retention and Co57 transmission). With dual isotope imaging, these spot markers will allow alignment of images for more accurate determination of regional deposition/retention. These very low radiation sources have been obtained from commercially available home smoke alarms. The placement of these markers will be determined to be outside the lung field during the transmission scan. Their location will be marked in semi-permanent ink for later placement during Tc99m deposition/retention scans. The shielded side of this source will be placed/taped onto the subject's skin. Radiolabeled Tc99m-sulfur colloid will be delivered using a modified Pari-LC Star nebulizer (MMAD 9.5 um). This is a closed delivery system that produces 80 ml/sec air flow, and therefore limits the inspiratory flow rate to this value. While seated in front of a gamma camera subjects will perform single inhalations lasting ~10 seconds each from the delivery system and will exhale at 500 ml/sec (using feedback from a flow meter in the breathing circuit). Approximately 5 of these inhalation maneuvers will be required to deposit an adequate isotope dose to the lung. Subjects will be allowed to breathe normally (off the nebulizer) in between each inspiratory maneuver. Each volunteer will practice these maneuvers prior to the actual radio-aerosol inhalation to guarantee his/her proficiency. The activity of Tc99m-SC loaded in the nebulizer will be adjusted to provide an estimated 40 uCi deposited in the lung for the MCC/CC scan. Patients between the age 12-18 years old will receive ¼ of the adult dose to account for the smaller lung volume. A single crystal detector will be placed at the subject's back during inhalation to monitor dose to the lung. Total inhalation time should be less than 5 minutes in all cases. Immediately following isotope inhalation, the subject will gargle and drink water to clear activity that deposited in the mouth into the stomach. The subject will then (within a minute of final inhalation maneuver) be seated in front of a large-field-of-view gamma camera to begin acquiring consecutive 2 minute images. The first two-2 minute images will provide initial, time zero activity (i.e. 100% retention) followed by the same imaging at the start of every 10-minute period until 1 hour has passed to assess baseline MCC. Subjects will then inhale 4 puffs of albuterol from the MDI inhaler and consecutive 2 min imaging continues for the next hour to assess the effect of albuterol on MCC. PFTs will then be performed and subjects will cough a total of 30 times over a 30-minute period to assess CC by gamma imaging over that period. Finally, a static 15-minute image will be measured at 6 hours (±30 minutes) after the initial radio-aerosol deposition scan. (See table of procedures in section 4.1).

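### The Aim 3 cough endpoint has two definitions that do not match: a 120-to-150 min retention change, and a formula that uses a 60–120 min average and an undefined Ave150Clr

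*Combined protocol and SAP*

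**What the plan says.** Section 9.3, Aim 3, gives the outcome in words: "Cough clearance will be measured as the change in retention between 120 and 150 min post deposition". The following sentence gives a formula for what it treats as the same quantity: "This change between Ave120Clr and Ave150Clr will be tabulated for each PCD group". The result is tested against zero within each PCD group and then between the two groups, two-sided at 0.05.

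Elsewhere only the formula appears. The synopsis lists "Change in MCC following cough clearance: Ave150Clr-Ave120Clr" among the outcome measures, and its analysis summary states that "the change pre- to post-cough clearance (Ave150Clr-Ave120Clr) will be calculated for each subject". Section 4.1 Outcome Measures uses the same difference and labels it tertiary/exploratory.

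Section 9.1 computes Ave60Clr and Ave120Clr as means of the 10-minute clearance values over 0–60 and 60–120 min. It says the average is taken over every 10-minute point "rather than simply reporting a clearance value at a single time, and represents the average clearance at the midpoint of each period". The abbreviations list glosses Ave120Clr as "Average Clearance at 120 minutes". Neither place mentions Ave150Clr.

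Two imaging details bear on this. Section 8 (MCC procedures) takes the first two 2-minute images as 100% retention, and it describes 30 coughs over 30 minutes with gamma imaging across that time. The table of procedures in Section 4.1 Treatment Design shows a single 4-minute scan once PFT and coughing are finished.

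**The concern.** The verbal definition is a difference between two time points that bracket the coughing. The formula subtracts a 60–120 min average from a quantity that the plan does not define.

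If clearance is always measured from time zero, which Section 8 supports, the formula starts counting at about 90 min. MCC between 90 and 120 min, before any directed coughing, is then scored as cough clearance. The plan expects MCC to be higher in the mild group and also expects better cough clearance there (Section 9.3, expected results), so the extra part runs in the direction of the hypothesis. If each window is instead re-zeroed at its own start, the formula subtracts MCC and pushes the other way.

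Both planned tests are affected, and nothing prevents the choice between definitions from being made after the data are seen.

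**Working it through.** The plan gives no effect size, SD or power for Aim 3, so there is no figure to reproduce. The mismatch follows from the text; the arithmetic below only shows its possible size.

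**Inputs from the plan.** Expected Ave60Clr is 3.6 (SD 2) mild and 0.5 (SD 0.25) severe (Section 9.6). There are 12 subjects per PCD group (Section 9.2). Image times come from the Section 4.1 table.

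**Assumptions.** Clearance is linear from time zero, C(t) = kt. There is no albuterol effect, and true cough clearance is equal in the two groups. On Section 9.1's midpoint reading, Ave60Clr = C(30), so k = Ave60Clr/30: 0.12 per min mild and 0.0167 severe. Likewise Ave120Clr = C(90).

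**MCC contained in each version of the endpoint (percentage points)**

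| Version | Expression | Mild | Severe | Mild − severe |
|---|---|---|---|---|
| Formula, Ave150Clr = 120–150 average | C(135) − C(90) = 45k | 5.40 | 0.75 | 4.65 |
| Formula, Ave150Clr = 150-min value | C(150) − C(90) = 60k | 7.2 | 1.0 | 6.2 |
| Stated retention change | C(150) − C(120) = 30k | 3.6 | 0.5 | 3.1 |
| Same, at the table's image times | C(146) − C(122) = 24k | 2.88 | 0.40 | 2.48 |
| Formula, windows re-zeroed, average | 15k − 30k | −1.80 | −0.25 | −1.55 |
| Formula, windows re-zeroed, end value | 30k − 30k | 0 | 0 | 0 |

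Table times are cumulative minutes minus 60, the start of the MCC scan. The post-albuterol scan ends at 124 min and the post-cough scan runs from 144 to 148 min. With 4-minute image pairs the centres are 122 and 146 min.

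**A null case.** If nothing clears after 120 min, the retention change is 0. The time-zero formula still gives C(120) − C(90) = 30k, which is 3.6 mild and 0.5 severe. An exponential curve fitted to the 10–60 min points gives about 2.4 and 0.35.

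**Sensitivity to curve shape (mild − severe: formula with average / formula with 150-min value / retention change)**

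- Saturating at a 10% plateau: 0.65 / 0.70 / 0.14
- Saturating at 20%: 2.23 / 2.79 / 1.18
- Saturating at 50%: 3.58 / 4.67 / 2.21
- Linear, mild rate doubled to 0.24 per min after albuterol: 10.8 − 0.75 = 10.05 / 14.4 − 1.0 = 13.4 / 7.2 − 0.5 = 6.7

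**Rejection rate of the nominal 5% between-group test.** Linear time-zero model, n = 12 per group, the plan's Ave60Clr SDs, equal cough means, assumed cough SD as shown, 40,000 simulated trials per cell:

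| Version | SD 2 | SD 4 | SD 8 |
|---|---|---|---|
| Formula, average | 96% | 67% | 26% |
| Formula, 150-min value | 99% | 84% | 40% |
| Retention change, 30 min | 84% | 40% | 15% |
| Retention change, table times | 71% | 28% | 11% |
| Retention change minus 60–120 min slope | 5% | 5% | 5% |

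Moving to the stated definition removes only the pre-cough part. MCC during the cough window remains.

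**The case against.** The strongest reply is that this is a notation slip. Section 9.3 states the intended quantity in plain words, and the abbreviations list can be read as making Ave120Clr a value at 120 min. That is plausible, but Section 9.1 applies to all aims and rejects single-time values, and Aim 2 uses the same symbol as a 60–120 min average. If a slip is the explanation, the text still needs correcting.

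Several points about size do stand:

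- **Direction is not established.** Linear time-zero clearance puts mild Ave120Clr at 0.12 × 90 = 10.8 even without albuterol, whereas Section 9.6 expects 7.2 after it. Re-zeroing at 60 min with a doubled rate gives 0.24 × 30 = 7.2. Section 9.6 labels that value Ave60Clr, so it is not decisive, but the reference point is unclear.
- **The linear curve is at the upper end** among the shapes tried without an albuterol effect. With the 10% plateau, rejection under the formula is only about 12–13%, 7% and 5% at the three SDs, ignoring between-subject spread in MCC. All cough SDs are assumed.
- **Averaging convention matters.** With six points per hour (midpoint 35 min), the linear differences shrink to 3.99 or 4.87 against 2.66.
- **MCC during coughing is a separate limitation.** It is present under either definition. Only the increment belongs to this point: 1.55 to 3.1 points in the linear model, about 0.5 with the plateau.
- **The imaging conflict may be narrow.** Imaging over the cough period could mean scans on either side of it, leaving 24 minutes in the table against 30 in the text.

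**Conclusion.** The concern holds. The plan equates two different quantities and leaves one term of its formula undefined; this conclusion needs no modelling assumption. The size and sign of the discrepancy do need assumptions. With linear time-zero clearance at the planned means, the formula overstates the mild-minus-severe difference by 1.55 or 3.1 points relative to the stated definition. With re-zeroed windows it falls short by 4.65 or 3.1 points. Early saturation makes the gap small.

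The stakes are limited. Aim 3 is tertiary/exploratory, has no sample-size basis, and does not touch the primary or secondary outcome. It should be corrected before analysis.

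**What to change.** Use one definition throughout: cough clearance = 100 × (R120 − Rpost). R120 is retention in the last image before PFT and directed coughing (end of row 7 of the Section 4.1 table), Rpost is retention in the post-cough scan (row 9), and both are relative to time-zero activity. Delete Ave150Clr − Ave120Clr from the synopsis, Section 4.1 Outcome Measures and Section 9.3, and align the abbreviations entry for Ave120Clr with Section 9.1. Reconcile the table's single post-cough scan with Section 8's imaging over 30 minutes.

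State that the endpoint still includes ordinary MCC during the cough window, so a mild-versus-severe difference cannot be attributed to cough alone. An optional sensitivity analysis would subtract the MCC expected from each subject's 60–120 min slope.

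The cost is wording, plus the sensitivity analysis if adopted; the table already includes both scans. There is a price in noise. A two-image difference has error SD √2 = 1.41 times the per-image SD, against √(1 + 1/6) = 1.08 for the formula with one post-cough image. Slope adjustment over 24 min raises it to √(2 + 576/1750 + 1200/1750) = 1.74. It also assumes that the post-albuterol rate continues, and it over-subtracts if clearance is flattening.
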